13.5.2 Randomisation Procedure

Once a subject is determined eligible for the study and informed consent has been obtained, each subject will be enrolled as soon as possible and will be assigned a unique study identifier; this will be used throughout the subjects' participation in the study, and will be documented on the enrolment

log. This number will be a numerical value commencing at '001', and as the study is single centre it will ascend sequentially thereafter.

Randomisation codes will be generated and secured by an independent statistical consultant from Fisher Clinical Services. The Investigator or designee will open a pre-sealed envelope containing the randomised treatment group allocation.

Randomisation must take place within two hours of hospital admission. Randomisation details will be documented on the enrolment log.

In the event that replacement supplies are required (e.g. due to more than one hour passing following reconstitution of the IMP) the investigator or designee should immediately contact Barts Health Pharmacy, who will quarantine the unused IMP as per their standard operating procedures. As the randomisation allocation is provided in pre-sealed envelopes and the IMP administrator is unblinded, replacement IMP will be prepared as per the original randomisation allocation provided in the pre-sealed envelope.

13.5.3 Cohort allocation/sequential allocation

N/A

13.6 Blinding

The trial participant, clinical team providing treatment (including pharmacy), and research investigators will be blinded to treatment group allocation. In addition, outcome assessors and data monitoring committees will also remain blind to group allocation.

However, due to the slight difference in opalescence of the IMP solution and placebo, and the requirement to visualise the IMP to confirm adequate re-constitution (see Section 15.12), it is not possible to blind the IMP administrator. Therefore, the IMP administrator, who will prepare the active ingredient IMP or placebo (diluent only), will be un-blinded.

In order to maintain blinding of the subject and clinical team, the IMP and placebo will be prepared in a separate room to the clinical team (Section 15.12). The administrator will simulate the time taken to re-constitute the IMP (6 minutes) when preparing the placebo, and administer it in a similar manner (i.e. as an intravenous injection over 1-2 minutes, given within the specified time-frame of one hour).

In order to maintain blinding of research investigators collecting follow-up data, a rota will be drawn up such that the investigator who administered the IMP/placebo will not be involved in collecting follow-up information for that subject. Our centre and its research team operate to a rota that has successfully conducted such clinical trial protocols previously.

Final unblinding of all trial participants will occur after creation of a locked analysis data set.

13.7 Unblinding

Unblinding of the treatment allocation is only allowed for safety concerns in an emergency situation.

Un-blinding or code breaks is the responsibility of the PI or Co-Investigator (medically qualified delegated deputy). However due to the emergency nature of the trial, it is important that the treating physician, has rapid unblinding access.

Sealed unblinding envelopes will be provided to the sites along with the study pack. The sealed unblinding envelopes will be stored in the Trauma Research Office in a secure area.

The treating physician will have the authority to request and un-blinding if the Safety of the participant is at risk. Any research team member can perform an un-blinding on the authority of a treating physician.

On receipt of the treatment allocation details the PI or treating physician will continue to deal with the participant's medical emergency as appropriate.

It is important that the unblended staff only divulge the treatment allocation to individuals on a strictly need to know basis.

Any un-blinding episode is classes as adverse event. The investigator must assess the relationship of the AE/SAE to the study drug. In all cases the CI and monitor must be notified within 24 hours after the code has been broken.

The breaking of the code (but not the result) and the reasons for doing so must be documented in the CRF, and medical notes. Written information will be disseminated to the Data Safety Monitoring Committee for review in accordance with the DMC Charter.

The blind will be maintained, where appropriate, for staff involved in data analysis and interpretation. It is important that the PI only divulges the treatment allocation to individuals on a strictly need to know basis.

The un-blinding envelopes will be monitored to ensure security throughout the study.

13.8 Trial Schedule

13.8.1 Schedule of Treatment for each visit

The following procedures will be conducted after arrival of the subject at the hospital.

Screening:

- Assess eligibility (refer to inclusion/exclusion criteria).
- Check that written agreement has been given to participate in the study in the form of a signed and witnessed informed consent form.
- Review medical and trauma history.
- Pregnancy test: by either urinary, serum, or point-of-care (see Fromm *et al.* 2012) testing of human chorionic gonadotrophin (hCG) for women of childbearing age.
- Vital signs (heart rate, blood pressure, respiration rate, oxygen saturations, body temperature, Glasgow Coma Score GCS).
- Dispense IMP in accordance with the randomization sequence.

Dosing:

• Body weight

- IMP administration
- Obtain blood samples for PK/PD analysis
- Monitor AEs and SAEs.

The following procedures will be conducted after dosing of the subject.

0 to 12 hours

- Blood sampling for PK/PD analysis
- Record baseline arterial blood gas.
- Monitor and record AEs and SAEs.
- Sequential organ failure assessment (SOFA) score.
- Renal injury, as per the risk, injury, failure, loss of function, endstage renal failure (RIFLE) score.
- Lung injury as per the Berlin definition.
- Infection rate.
- Number of ventilation free days.
- Renal Replacement Therapy (RRT) days.
- Vasopressors days.
- Composite time to complete organ failure (CTCOFR) score.
- Total length of critical care stay.
- Total length of hospital stay.

0 to 48 hours:

- Monitor and record AEs and SAEs.
- Record safety blood results.
- Record 24 hour fluid and transfusion requirements.
- Record concomitant medications.
- Sequential organ failure assessment (SOFA) score.
- Renal injury, as per the risk, injury, failure, loss of function, endstage renal failure (RIFLE) score.
- Lung injury as per the Berlin definition.
- Infection rate.
- Number of ventilation free days.
- Renal Replacement Therapy (RRT) days.
- Vasopressors days.
- Composite time to complete organ failure (CTCOFR) score.
- Total length of critical care stay.
- Total length of hospital stay.
- Record whether patient is alive and free of multiple organ failure (SOFA <5) at 48 hours

49 hours to Day 7:

- Monitor AEs and record SAEs.
- Record safety blood results.
- SOFA score.
- Renal injury, as per the RIFLE score.
- Lung injury as per the Berlin definition.
- Infection rate.
- Number of ventilation free days.
- RRT days.

- Vasopressors days.
- CTCOFR score.
- Total length of critical care stay.
- Total length of hospital stay.

Day 8 to Day 14:

- Monitor AEs and record SAEs.
- Record safety blood results (day 14 +/- 1).
- Renal injury, as per the RIFLE score.
- Lung injury as per the Berlin definition.
- Infection rate.
- Number of ventilation free days.
- RRT days.
- Vasopressors days.
- CTCOFR score.
- Total length of critical care stay.
- Total length of hospital stay.

Day 15 to Day 28:

- Monitor AEs and record SAEs.
- Record safety blood results (day 27 +/- 1)
- Renal injury, as per the RIFLE score.
- Lung injury as per the Berlin definition.
- Infection rate.
- Number of ventilation free days.
- Total length of critical care stay.
- Total length of hospital stay.
- Mortality status.

Until discharge:

- Number of ventilation free days.
- Total length of critical care stay.
- Total length of hospital stay.
- Mortality status.

Day 90 (Follow-up):

• Mortality status.

13.8.2 Schedule of Assessment (in Diagrammatic Format)

ASSESSMENT	SCREENING	RANDOMISATION/DOSING	FOLLOW-UP ASSESSMENTS						
	0-4HRS	0-4 HRS	0-12 HRS	13-48 HRS	49 HRS -DAY 7	DAY 7- 14	DAY 15 - 28	DISCHARGE	DAY 90**
Confirm eligibility	Х								
Informed Consent	Х								
Demographic Information	Х								
Pregnancy Test	х								
Medical History	х								
Vital signs	х								
Body Weight		Х							
Study Treatment		Х							
PK/PD Sampling*		Х	Х						
Safety bloods sampling*			Х	Х	Х	Х	Х		
Monitor AEs			X	X	X	Х	Х		
Monitor SAEs			Х	X	Х	Х	Х		

Version 2.0 TOP-ART
Concomittant medications		Х	Х					
SOFA Score		Х	Х	x				
Renal injury		Х	Х	х	Х	Х		
Lung injury		Х	Х	x	Х	Х		
Infection rate		Х	Х	x	Х	Х		
Mechanical ventilation days		Х	Х	Х	Х	Х	х	
RRT days		Х	Х	х	Х			
Vasopressors days		Х	Х	х	Х			
CTCOFR Score		Х	Х	х	Х			
ACCU length of stay		Х	Х	х	Х	Х	х	
Hospital length of stay		Х	Х	х	Х	Х	х	
Mortality Status						Х	х	Х
Alive and free of MOF			Х					

*Please See section 13.8.3 for detailed PK sampling and clinical bloods sampling time points.

**End of Study

13.8.3 Trial assessments

Medical History

The medical and trauma history will be conducted at screening and should include (but not be limited to) demographic information, subjects' medical history with an emphasis on the trauma, current medication, past medication and allergies. This will be ascertained as part of the subjects' initial clinical assessment by the trauma team, and the Trauma Research Fellow. The known medical history must be documented in the subject's notes (the on-site source document) prior to IMP administration and also recorded in the CRF. Any further medical history ascertained subsequent to the initial assessment will be derived from the subjects' notes during the assessment phase.

Vital signs

Vital signs will be recorded at baseline and at PK/PD sampling points. They will also be monitored for 28 days as part of the SAE assessment process.

Systolic and diastolic blood pressures will be recorded using a standard sphygmomanometer reading or by invasive arterial monitoring (where this has been inserted as part of routine clinical care). Pulse rate and oxygen saturations will be measured by pulse oximetry or by arterial monitoring as above. Respiration rate will be assessed by observation as breaths per minute; and a tympanic body temperature measure will be used, unless other methods (e.g rectal monitoring) are in place for continuous clinical monitoring. GCS will be recorded from the subject notes or assessed clinically.

Pregnancy test

Prior to administration of any IMP a pregnancy test will be undertaken on all women of childbearing potential.

Note: The subject must not be dosed if any tests are positive.

Body weight

Body weight will be estimated to the nearest 10kg.

PK/PD Blood samples

Subjects will have 10mls of blood drawn to determine the plasma levels of Artesunate and its metabolite DHA (PK-PD study in man) at the following time points:

- At hour 0 (within 10 minutes) immediately prior to IMP dosing
- 5 (±1 minute) minutes after the start of IMP infusion
- 30 (±2 minutes) minutes after the start of IMP infusion
- 1 (±5 minutes) hours after the start of IMP infusion
- 4 (±20 minutes) hours after the start of IMP infusion
- 12 (±30 minutes) hours after the start of IMP infusion

The total 60 mls of blood sampled equates to approximately 1% of the total circulating blood volume over the 12-hour period. As recruited patients will be receiving blood transfusions as part of their standard clinical care during this time, it is not anticipated that the samples taken will have any

adverse effects on clinical outcomes. Blood that is collected and not used for PK/PD analysis will be processed and stored for use in ancillary research (See Section 13.3.9)

Clinical Blood Sampling

In order to calculate SOFA and RIFLE scores, ascertain presence of infection, and degree of shock on admission, record will be made the following parameters as part of routine clinical bloods (i.e. no additional specific research blood draws will be taken):

- Platelets
- Creatinine
- Estimated Glomerular Filtration rate (eGFR)
- Bilirubin
- Total white blood cells
- Neutrophils
- Lymphocytes
- C-reactive protein
- Arterial or venous blood gas result (admission result only)

In addition, in order to ensure adequate safety of the IMP, the following will be monitored and for the purposes of safety monitoring for AEs and SAEs:

- Haemoglobin
- Haemocrit
- Red cell count
- Mean cell volume
- Mean corpulscular haemoglobin (MCH)
- Red blood cell distribution width (RDW)
- Mean corpuscular haemoglobin concentration (MCHC)
- White cell count
- Platelet count
- Neutrophils
- Lymphocytes
- Monocytes
- Eosinophils
- Basophils
- Alanine aminotransferase (ALT)
- Aspartate aminotransferase (AST)
- Alkaline phosphate
- Gamma-glutanyl transpeptidase (GGT),
- Bilirubin
- Creatinine
- Urea
- Sodium
- Potassium
- Calcium
- Albumin
- Prothrombin Time
- International Normalised Ratio (INR)

These parameters will be collected daily for days 1-7, and subsequently on day 14±1, day 21±1, and day 27±1, provided the subject is still in hospital. Where possible, these data will be collected from

routine clinical bloods. In the event they have not been undertaken as part of routine clinical bloods, the research fellow will take the bloods at the specified times (unless the subject declines).

Radiological Investigation Results

Radiological investigations (including Chest X-rays and CT scans) undertaken as part of a subjects' clinical course, will be examined for calculation of ARDS scores as well as for assessment of adverse events. No specific radiological investigations will be undertaken for research purposes.

Outcome Measures

Please see Appendix 2 for a full description of the outcome measures that will be recorded, including: SOFA Score, Renal injury (RIFLE Score), Lung Injury (ARDS Score), Infection rate, and days of organ failure (CTCOFR score).

Ventilator free days will be calculated by the subtracting the number of days spent on mechanical ventilation from 28.

Renal replacement therapy days will be calculated as the number of days spent on haemodialysis or haemofiltration.

Vasopressor days will be calculated as the number of days spent on ionotropic drugs, including for instance noradrenaline, dobutamine, vasopressin.

Length of stay will be recorded in days, for the total number spent in ACCU and in Hospital.

Mortality will be recorded at 28 days, discharge and 90 days.

At 48 hours it will be recorded whether the patient was alive and free of multiple organ failure (defined as SOFA≤5).

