11.3 Endpoints

11.3.1 Primary Endpoint

The primary efficacy endpoint is reduction in SOFA score at 48 hours for Artesunate treatment arm versus placebo.

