11.3.2 Secondary Endpoint

The secondary endpoints are:

- Maximum SOFA score: Maximum SOFA score over 7 days.
- Mean SOFA Score (Days 2-5).
- Prolonged organ failure: Defined as SOFA>5 on Day 7.
- Days on organ support: As per the CTCOFR score (Nadel *et al.*, 2007).
- Incidence of acute lung injury: As per Berlin definition (ARDS Task Force, 2012).
- Incidence of acute kidney injury: As per the RIFLE score (Bellomo *et al.*, 2004).
- Incidence of infection: As per definitions of infection by (Cole *et al.*, 2014).
- Number of ventilation free days.
- Total length of hospital stay.
- Total length of critical care stay.
- Mortality (discharge, 28 day and 90 day).
- Alive and free of multiple organ failure (defined as SOFA <=>) at 48 hours.

The safety endpoint is the serious adverse event rate in the first 28 days.

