APPENDIX 2: SCORING SYSTEMS AND DEFINITIONS

PARAMETER	SCORE BREAKDOWN				
	0	1	2	3	4
PaO2/FiO2 ratio	>53.3	≤53.3	≤40	≤26.7	≤13.3
Platelets	≥150	<150	<100	<50	<20
Bilirubin	<20	20-32	33-101	102-204	>204
CVS	MAP	MAP<70	Dopamine ≤5	Dopamine >5 or	Dopamine >15 or
	≥70		or any dose	adrenaline ≤0.1 or	adrenaline >0.1 or
			dobutamine	noradrenaline	noradrenaline >0.1
				≤0.1 mcg/kg/min	mcg/kg/min
GCS	15	13-14	10-12	6-9	<6
Creatinine	≤109	110-170	171-299	300-440 or urine	>440 or urine
				<500ml/day	<200ml/day

1. SOFA Score Parameters (Vincent et al. 1998)

2. CTCOFR Scoring parameters (Nadel et al. 2007)

PARAMETER	DESCRIPTION	
Last day vasoactive agent	dobutamine <5 μg/kg/min or cessation of	
	adrenaline/noradrenaline/phenylephedrine or other	
	vasoactive agent	
Last day mechanical ventilation	IPPV, CPAP, Bimodal	
Last day renal replacement therapy:	peritoneal dialysis, haemodialysis, ultrafiltration,	
	haemofiltration	
For each parameter score 1 point per day up to 14 days		
Total CTCOFR Score if composite >14 days = 15 points		
Total CTCOFR Score if death during study (28 days) = 16 points.		

3. RIFLE Score Parameters (Bellomo et al. 2004)

	EGFR/SERUM CREATININE (Cr)	URINE OUTPUT
Risk	Cr x 1.5 or; eGFR decrease by >25% <0.5ml/kg/h for	
Injury	Cr x 2 or; eGFR decrease by >50%	<0.5ml/kg/h for 12 hours
Failure	Cr x 3 or; GFR decrease by >75% or; If baseline Cr	<0.3ml/kg/h for 24 hours
	>353.6 µmol/L, increase of 44 µmol/L	or; anuria for 12 hours
Loss of function	Complete loss of function >4 weeks	
End-stage kidney	Complete loss of function > 3 months	
disease		

4. Acute Lung Injury Definitions (ARDS Task Force, 2012)

THE BERLIN DEFINITION OF ACUTE RESPIRATORY DISTRESS SYNDROME		
TIming	<1 week of a known clinical insult or new or worsening respiratory symptoms	
Chest Imaging ^a	Bilateral opacities not fully explained by effusions, lobar/lung collapse,	
	nodules	
Origin of	Respiratory failure not fully explained by cardiac failure or fluid overload.	
Oedema	Need objective assessment (e.g. echocardiography) if no risk factor present.	
Oxygenation:		
Mild	200mmHg <pao2 cpapb ≥5 cmH2O</pao2>	
Mod	100mmHg <pao2 cmh2o<="" fio2="" peep="" td="" with="" ≤200mmhg="" ≥5=""></pao2>	
Severe	PaO2/FiO2 ≤100mmHg with PEEP ≥5 cmH2O	
a: Chest radiograph or Computed Tomography scan		
b: This may be delivered non-invasively in the mild acute respiratory distress syndrome		

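### The protocol limits the recorded blood gas to admission and provides for no later PaO2 or FiO2, although the 48-hour SOFA and Berlin ARDS are scored on PaO2/FiO2

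*Protocol*

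**What the plan says.** The primary endpoint in Section 11.3.1 is SOFA at 48 hours: "The primary efficacy endpoint is reduction in SOFA score at 48 hours for Artesunate treatment arm versus placebo". Section 11.3.2 adds "Maximum SOFA score over 7 days", mean SOFA over days 2-5, prolonged organ failure on day 7, acute lung injury by the Berlin definition, and being alive and free of multiple organ failure at 48 hours.

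Section 13.8.3 (Clinical Blood Sampling) opens its first list with "In order to calculate SOFA and RIFLE scores, ascertain presence of infection, and degree of shock on admission, record will be made the following parameters". The list comes from routine care, and "no additional specific research blood draws will be taken". Its last item is "Arterial or venous blood gas result (admission result only".

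A second list, for safety, follows. It has no blood gas. After it comes the timing clause: "These parameters will be collected daily for days 1-7, and subsequently on day 14±1, day 21±1, and day 27±1".

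In the visit schedule of Section 13.8.1 the only gas item is "Record baseline arterial blood gas", under 0 to 12 hours. The assessment table in Section 13.8.2 has no blood gas row.

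Appendix 2 gives "PaO2/FiO2 ratio" as the respiratory row of the SOFA table, scored 0 to 4, and uses the same ratio for the Berlin oxygenation grades.

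**The concern.** The rule on what is recorded and the definition of the endpoint do not meet. The list written partly to supply SOFA limits its one oxygenation item to admission and lets a venous sample stand in, while the primary endpoint needs an arterial value and an inspired oxygen fraction at 48 hours.

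Staff who follow the recording text closely have three ways to complete the respiratory component: leave it blank, score it 0, or fill it where an arterial gas happens to be in the notes. The third ties completeness to severity, because an arterial sample is more likely in a sicker or ventilated patient. Scoring 0 lowers the total in patients with poor oxygenation and can move them across the threshold of 5 that defines two of the secondary endpoints. A treatment that changed how many patients are ventilated would also change how many have the component measured.

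**Working it through.** This is a comparison of sections. The protocol states no figure for this point that could be reproduced.

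**Size of the component.** The SOFA table in Appendix 2 has six rows, each scored 0 to 4. The maximum is 6 × 4 = 24. Respiration contributes up to 4 of 24, one sixth of the range. Without it, 5 × 4 = 20 points can be scored.

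**Where each blood-based SOFA input is recorded after admission.**

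| SOFA input | First list, 13.8.3 | Daily safety list, days 1-7 | Back-up draw if not done routinely |
|---|---|---|---|
| Platelets | yes | yes | yes |
| Bilirubin | yes | yes | yes |
| Creatinine | yes | yes | yes |
| PaO2 | admission gas only, arterial or venous | no | no |

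The blood gas is the only one of the four that is limited to admission. If the daily timing clause is read as covering both lists, the gas line still carries its own restriction.

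**Arterial or venous.** Section 13.8.1 asks for an arterial baseline gas and Section 13.8.3 accepts either. A venous gas does not give a PaO2, so the two sections differ even at baseline.

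**FiO2.** It appears in the abbreviations and in the Appendix 2 definitions, but on no list of items to record for SOFA or Berlin.

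**Time points that need the ratio.** Sections 13.8.1 and 13.8.2 schedule SOFA from 0 hours to day 7 and Berlin lung injury from 0 hours to day 28. Later PaO2/FiO2 values therefore enter the 48-hour SOFA, freedom from organ failure at 48 hours, maximum SOFA, mean SOFA over days 2-5, day-7 SOFA, and ARDS. For Berlin, Section 13.8.3 says that clinical chest imaging will be examined; it has no matching sentence for oxygenation.

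**What scoring 0 would do to one patient (hypothetical values).** Five components total 4 and the true respiratory score is 3. The full SOFA is 4 + 3 = 7, above 5. With respiration set to 0 it is 4, which meets the definition of free of multiple organ failure in Section 11.5 (5 or less).

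**Sections that might supply the value.** Section 13.8.3 (Outcome Measures) says that the Appendix 2 measures will be recorded but sets no timing for a gas. Section 20.6 names medical notes, observation charts and electronic laboratory results as source data but does not say that later gases are taken from them. Section 19.11 allows imputation of missing outcomes, which is no substitute for recording values that are already charted. None of the three lifts the admission limit.

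**The case against.** The strongest reply is that the list in Section 13.8.3 is not the full set of SOFA inputs. It covers routine bloods only, and it also omits mean arterial pressure, GCS, vasopressor dose and urine output, all of which SOFA uses. The absence of FiO2 from a blood list therefore shows little. One stated purpose of the list is degree of shock on admission, and an admission gas, arterial or venous, fits that purpose exactly. SOFA and Berlin are scheduled in later windows, charts and laboratory records are named as sources, and nothing forbids taking later gases from them. The CRF and SAP, which are not at hand, may settle the rest.

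Most of this stands. A reader might infer that the 48-hour SOFA cannot be scored at all, or that the protocol rules out using later gases. The text supports neither: it restricts one item in one list and does not bar chart abstraction.

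What does not fall away is the difference between silence and a restriction. Pressure, GCS and vasopressors are simply not on a blood list. The gas is on the list, under a heading that names SOFA, with a limit that excludes the time of the primary endpoint. A SAP can say how to handle a missing component, but it cannot bring back values that were not recorded.

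**Conclusion.** The point holds as an inconsistency in data specification between Sections 13.8.1 and 13.8.3 and Appendix 2. It bears on the primary endpoint and should be corrected. It affects one of six components, 4 of 24 points, at every SOFA time point after admission, and the oxygenation criterion for ARDS.

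How much data would be lost is unknown. That depends on how often arterial gases are taken in routine care and whether staff abstract them, and the protocol gives neither. The link between having an arterial sample and severity is a clinical expectation, not a protocol figure.

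A reader might also infer a definite loss of power. The documents do not support one. The direction depends on how much of the 2-point effect in Section 19.1 lies in the respiratory component and on how the SD of 3.43 changes when that component is lost. Neither is stated, and depending on the assumption power could fall, stay the same or rise. The sample size figures are not in question here.

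**What to change.** Reconcile Sections 13.8.1 and 13.8.3 with Appendix 2:

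- State that the admission-only limit applies to the assessment of shock on admission, not to SOFA or Berlin.
- Record charted PaO2 and FiO2 at the 48-hour assessment, daily on days 1-7 for SOFA, and at the Berlin time points to day 28, and say which value is used when there are several.
- State that a venous gas does not supply PaO2, and align the baseline wording of the two sections.
- Fix one rule for scoring respiration when no arterial sample exists, set before unblinding and the same in all arms. The documents do not favour any particular rule, so the choice belongs to the trial team.

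The cost is about two CRF fields filled from existing charts, with no extra blood draws, plus a short protocol amendment.
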